#### Appendix A: Comments and rebuttal letter Journal of Cardiac Failure

## Fluid REStriction in Heart failure versus liberal fluid UPtake: Rationale and design of the randomised FRESH-UP study.

We thank the statistical reviewer for the critical appraisal of our manuscript. In response to the comments, we adjusted the manuscript and feel that the quality has improved substantially. Please find below a point-by-point response to the reviewer' comments.

#### **Statistical Reviewer Comments:**

#### **Summary Statement:**

The authors submitted a paper that provided the rationale and design of the FRESH-UP study, a randomized, controlled, open-label trial that seeks to determine the effectiveness and safety of liberal fluid intake vs. fluid restriction on QoL in outpatient HF patients over a 3-month period.

#### **Major Concerns:**

1. Some correction for multiplicity of hypothesis testing on the two primary endpoints (KCCQ-OSS and TDS-HF) is needed in the statistical analysis plan. In the last paragraph of the Sample Size Calculation section, it initially appears that the authors are proposing hierarchical testing of the two endpoints. However, the authors write "In the case of non-significant findings for the first primary endpoint (KCCQ), the second primary endpoint will be tested at the 2-sided 5% significance level but will be regarded as an exploratory endpoint, and a nominal p-value will be produced." There are a few concerns. First, this deviation is not consistent with the hierarchical testing method used to protect inflation of the type I error rate. Second, TDS-HF is a primary endpoint and should not be switched to an exploratory endpoint after results for KCCQ-OSS become known. Third, how would such findings be communicated to the public? Please provide adequate control of type I error rate inflation. If adequate control cannot be provided, please consider TDS-HF as a key secondary endpoint. If KCCQ-OSS and TDS-HF are co-primary endpoints, then no multiplicity adjustment is needed since one would need to succeed on both endpoints in order to consider the intervention a success.

We thank the reviewer for the critical appraisal, which perfectly reflects the discussions we had during the design phase of the study. In line with the reviewer's suggestion, we have adjusted the primary and secondary endpoints. In the revised manuscript, the KCCQ-OS is the primary endpoint. The TDS-HF has been changed to a key secondary endpoint (abstract: page 3, line 14-15, manuscript: page 4, line 8 / page 5, line 22-24 / page 7, line 19 / page 8, line 15-17 and the Visual Take Home Graphic).

The KCCQ is a well validated and widely accepted questionnaire that can quantify the QoL (and its changes) in the heart failure population. Although, the TDS-HF is also validated and may quantify an important symptom as thirst. The questionnaire reflects only one aspect of the study and it may not be as established as the KCCQ.

We based our sample size calculation on the KCCQ-OSS, with adequate power and with just KCCQ-OSS as our primary endpoint there is no inflation of the type I error rate. Moreover, with simplification of the protocol with only KCCQ-OSS as the primary endpoint, the interpretation of the results of the trial will be much clearer for the public.

Accordingly, we feel that the quality of the study design and manuscript have improved due to your valuable suggestion.

2. The authors state that the intention-to-treat principle will be used for the primary analysis (re: Analysis populations section). However, the authors also state that "For the primary analysis, only those patients of whom both baseline and follow-up are available will be analysed." Written as such, the analysis population for the primary analysis is not the intention-

to-treat, since it does not include all randomized subjects. It is in fact a complete-case analysis. Please modify.

In accordance with the reviewer's rightful remark, we consider it important to include the ITT population in the primary analysis. We adapted the manuscript accordingly (page 7, line 21-22).

Therefore, we have proposed an analysis for which any missing baseline values are assumed to be missing completely at random and any missing follow-up values are assumed to be missing at random. For this, multiple imputation will be used to handle missing baseline, however unexpected, and outcome data on the KCCQ-OSS. We would like to refer to the answer on the next comment regarding handling missing QoL measurements.

3. The authors also state that sensitivity analyses will be performed to assess the impact of missing primary endpoints and suggested using multiple imputation (MI). There are a few concerns. First, MI assumes missing at random mechanism and missing QoL measurements are notoriously known to be missing not at random. Sensitivity analyses for non-ignorable missingness should be developed. Second, missingness due to death is not a missing data problem, since the outcome values do not exist and so, one should be cautious about using methods to impute these unobserved values. Third, the authors proposed single imputation for missing baseline scores. Why not multiple imputation for baseline scores? With MICE, one can develop a model for baseline scores and another model for 3-month scores that are dependent on the baseline scores (plus other auxiliary variables).

The reviewer has raised some important considerations related to the challenges related to the analysis of QoL data with missing values, and we agree with all of these concerns.

We do not expect any missing baseline QoL measurements because they must be completed before randomisation and are filled out in a digital manner in which completion is mandatory and entry errors are impossible. Besides, due to the method of scoring, the KCCQ will always provide an Overall Summary Score, based on a mean of the available other summary scores. For the unlikely case where a baseline value is missing, we have taken on the advice of the reviewer and proposed that multiple imputation is also used for these values (page 7, line 22-27).

Regarding the missing QoL measurements at follow up, it is agreed that the assumption that these data are missing at random is a strong assumption, and agree that sensitivity analyses for which these data are assumed to be missing not at random should be performed. We have now specified these in the protocol (page 8, line 3-6).

It is agreed that missing data due to death is not a missing data problem, however particularly for the KCCQ, which is predictive of clinical outcomes including death, excluding patients from the analysis who died is likely to bias the results. Therefore for our primary and sensitivity analyses we would like to retain the patients who died in the analysis. We will ensure that this issue is part of our discussion and keep an eye out for any emerging methodological research that may help to resolve this issue while allowing us to address the research question of interest.

4. The sample size calculation accounts for a 10% drop-out rate, increasing N from 454 subjects to 498 subjects. Can the authors clarify how 498 subjects were obtained? Applying the standard LTF adjustment, one gets around 506 patients (after rounding up).

We thank the reviewer for his/her suggestion and applied the LTF adjustment as suggested. We performed the calculation:  $N = n / (1-(z/100)) \rightarrow N = 454 / (1-(10/100)) = 504.4$ . Therefore, we adjusted the sample size to 506 subjects to maintain an equal distribution of subjects across both study arms (manuscript: page 9, line 12 / DSMB Charter: page 1, page 6, page 10 / Figure 1 and the Visual Take Home Graphic).

5. In the Data Safety Monitoring Board section, the authors write "The DSMB has two mandates. First, to perform two interim analyses when data is available of 33% and 66% of the patients for safety on the occurrence of the clinical endpoints....." This is not completely accurate since the DSMB charter lists "Early stopping due to harm of a treatment or clear

superiority" as one of the possible recommendations after an IA. Therefore, the IA consists of both efficacy and safety assessments especially since KCCQ scores (the primary endpoint) is listed as one the main parameters of interest for the DSMB. Since interim looks for efficacy on the primary endpoint will increase the type I error rate of a clinical trial, please clarify how the type I error rate will be controlled. Furthermore, it may no longer be the case that the significance level for the final analysis of the primary endpoint(s) will be at 0.05 (re: "Both primary hypotheses on QoL by the KCCQ-OSS and TDS-HF will be tested at a 2-sided 5% significance level.)

We agree with the reviewer that there is a discrepancy between the original manuscript and the DSMB charter. To be clear, the objective of the DSMB is to solely assess safety. Accordingly, we have adjusted the DSMB charter. There will be no interim analyses on efficacy. We have removed the KCCQ scores as parameters of interest from the DSMB charter to avoid any misunderstanding in this regard. In addition, we have adjusted the possible recommendation "Early stopping due to harm of a treatment or clear superiority" in the DSMB charter as well. The DSMB will assess safety based on clinical event rates. We thank you for addressing this inconsistency in our documents and feel that the revised version of the DSMB charter provides more clarity.

Since no interim analyses on efficacy will be performed, there is no increase in type I error rate and no additional measures are required to control type I error rate.

# 6. Based on prior experience, do the authors have a sense of cross-over rates (re: Discontinuation of study treatment section) between study arms? Why wasn't cross-over accounted for in the sample size calculation?

During the design phase of study we expected the rates of discontinuation of study treatment to be very low. In our experience, participants are highly motivated to adhere to the study protocol. As expected, most patients already adhere to the control therapy and are excited to particate in the interventional group. The drop-out rate of the control group is very low and there are, till further notice, no drop-outs in the interventional group. Our objective is to study the effect of a fluid advice in a real-world situation and a pragmatic design was chosen in which the cross-over rate was assumed neglectable. In addition, because the primary analysis is based on the intention-to-treat population we are essentially specifying a treatment policy estimand approach for the primary analysis, in which outcomes are measured regardless of whether patients divert from their advised fluid intake or not.

7. The authors acknowledged in the Limitations that patient-reported fluid intake at week 6 may not be reliable and yet this will form the basis of the per-protocol analysis. I worry about the utility of the per-protocol analysis if there will be misclassification on adherence. Is it feasible to record fluid intake daily? Furthermore, regardless of misclassification, per-protocol is a biased analysis and the authors may wish to consider causal inference methods (e.g., instrumental variable analysis) to address non-adherence.

We agree with the reviewer that the true fluid intake cannot be determined with full certainty. In that regard, we feel it is important to state that our primary analysis is based on an intention-to-treat principle. Our per-protocol analysis is only considered as an additional supporting analysis, but is indeed quite limited due to uncertainty on actual fluid intake.

It is essential to note that one of the main negative effects of a fluid restriction on QoL is the fact that patients need to monitor this on a day-to-day basis. The major upside of liberal fluid intake is the fact that there is no need to monitor this every day. Therefore, we do not want the patients in the intervention arm of liberal fluid intake to measure their intake for the whole study period. In addition, reporting daily fluid intake may even be more troublesome for patients which may lead to an increase in incorrect documentation of the actual fluid intake. Thus, we chose to ask patients for a dedicated week rather than the full study period.

We agree that a per-protocol analysis is biased given the potential for imbalance between the treatment arms and will explore alternative options for inclusion in the Statistical Analysis Plan. We thank the reviewer for referring us to causal inference methods and will explore this as an option.

#### **Minor Concerns:**

We thank the reviewer for the attention to details. We have changed the manuscript according to the remarks above.

1. Under Patients, the authors state that there are currently four participating centres. Please update the DSMB Charter as it notes 2 sites.

This has been corrected to 4 sites (DSMB Charter: page 1).

- 2. I assume that the composite clinical endpoint and AKI will be assessed at both 3 & 6 months and not only 6 months is this correct? If so, please make clear in Outcome section.
- The reviewer is correct and the manuscript has been adjusted accordingly (page 6, line 4).
- 3. Under Study Organisation, missing a word between "secondary" and "will": The review and adjudication of all secondary will be conducted by an independent event adjudication committee. This has been adjusted in the revised version of the manuscript (page 10, line 2).

TDS-HF Thirst Distress Scale for patients with HF

1. Administrative Information

1.1. Study identifiers

• Protocol: NL75112.091.20, version 4.2, 02-12-2022

• ClinicalTrials.gov register Identifier: NCT04551729

1.2. Revision history

	-		
Version	Date	Changes made to document	Authors
1.0	01-09-2023	Drafted version 1.0	[name]
			[name]
			[name]
			[name]
2.0	17-04-2024	Subanalyses added	[name]
		EQ-5D-5L missing value handling	[name]
			[name]
			[name]

1.3. Contributors to the statistical analysis plan

1.3.1.Roles and responsibilities

Names	Affiliation	Role on study	SAP contribution
[name]	Radboud University Medical Center,	Coordinating	Drafting the statistical
	department of Cardiology	investigator	analysis plan
[name]	Radboud University Medical Center,	Study statistician	Revisions
	department for Health Evidence		
[name]	Radboud University Medical Center,	Coordinating	Revisions
	department of Cardiology	investigator	
[name]	Radboud University Medical Center,	Principal investigator	Revisions
	department of Cardiology		

1.3.2.Approvals

The undersigned have reviewed this plan and approve it as final. They find it to be consistent with the requirements of the protocol as it applies to their respective areas. They also find it to be compliant with ICH-E9 principles and, in particular, confirm that this analysis plan was developed in a completely blinded manner (i.e. without knowledge of the effect of the intervention(s) being assessed).

[name] 18-04-2024 <signature> <date> [name] 17-04-2024 <date> <signature> [name] 18-04-2024 <signature> <date> [name]

[figure not shown]
<signature>

17-04-2024

<date>

2. Study synopsis

The FRESH-UP study is a randomised, controlled, open-label, multicentre trial to investigate the effects of a 3-month period of liberal fluid intake vs fluid restriction (1500 ml/day) on quality of life (QoL) in outpatients with chronic heart failure (HF).

2.1. Study objectives

2.1.1. Primary objective

To investigate the effect of liberal fluid intake versus standard fluid restriction (1500 ml/day) on QoL in outpatient chronic HF patients at 3 months after randomisation, as assessed by the Kansas City Cardiomyopathy Questionnaire Overall Summary Score (KCCQ-OSS).

2.1.2. Secondary objectives

To investigate the effect of liberal fluid intake versus standard fluid restriction (1500 ml/day) on:

- Thirst distress at 3 months after randomisation, as assessed with TDS-HF
- QoL at 3 months after randomisation, as assessed by KCCQ Clinical Summary Score (-CSS), each of the KCCQ domains and the proportion of patients with clinically meaningful changes in these scores, and the European Quality of Life Five Dimensions Five Levels questionnaire (EQ-5D-5L)
- Patient reported fluid intake at week 6
- Safety, as assessed by the composite of: death, all-cause hospitalisation and the requirement to apply iv-loop diuretics during the 6-month clinical follow-up duration.

2.1.3. Exploratory objectives

To investigate the effect of liberal fluid intake versus standard fluid restriction (1500 ml/day) on:

- Safety as assessed by (time to the first) occurrence of: death, all-cause or unplanned HF
 hospitalisation or the requirement of iv-loop diuretics during the 6-month clinical follow-up
 duration
- The (time to the first) occurrence of acute kidney injury defined as a 50% decline in estimated glomerular filtration rate relative to baseline, or decrease of >30 ml/min/1.73m2 and to a value below 60 ml/min/1.73m2 during the 6-month clinical follow-up duration
- Serum biomarkers (NT-proBNP, sodium, osmolality, haemoglobin, haematocrit) and weight at 3 months after randomisation
- The use of concomitant medication (diuretics in particular)

2.2. Patient population

2.2.1.Inclusion criteria

- Diagnosis of chronic HF with New York Heart Association (NYHA) class II/III according to the prevailing guidelines > 6 months prior to randomisation
- Adult (age ≥ 18 years)

2.2.2. Exclusion criteria

- Reversible cause of HF (thyroid disorders, severe anaemia, vitamin deficiencies)
- Hospital admission for HF within 3 months of randomisation
- Chronic HF with NYHA class I/IV
- Hyponatremia at baseline (sodium <130 mmol/l)
- Estimated Glomerular Filtration Rate (eGFR) of <30 ml/min/1.73 m2 at baseline
- Changes in HF medical therapy in last 14 days prior to randomisation
- Scheduled cardiac surgery within 3 months of randomisation
- Recent (within 3 months) coronary intervention (PCI or CABG) or implantation of pacemaker

device

- Comorbidity for which fluid restriction is advised by a different treating physician (e.g. nephrologist)
- Life expectancy of less than 6 months
- The treating clinician believes that participation in the study would not be in the best interests of the patient
- Inability to provide IC

2.3. Outcomes

2.3.1. Primary outcome

• QoL as assessed by KCCQ-OSS¹ at 3 months after randomisation

2.3.2.Secondary outcome

Key secondary outcome:

• Thirst distress as assessed by the TDS-HF¹

Other secondary outcomes:

- QoL at 3 months as assessed by KCCQ-CSS
- QoL at 3 months as assessed by each of the KCCQ domains and the proportion of patients with clinically meaningful changes in these scores
- QoL at 3 months as assessed by EQ-5D-5L¹
- Patient-reported fluid intake in week 6
- Safety: The composite clinical endpoint: death, all-cause hospitalisation and the requirement of iv-loop diuretics during the 6-month clinical follow-up duration

2.3.3. Exploratory outcomes

- Safety: The number of occurrences of: death, all-cause or unplanned HF hospitalisation or the requirement of iv-loop diuretics during the 6-month clinical follow-up duration
- Safety: The time to the first occurrence of: death, all-cause or unplanned HF hospitalisations or the requirement of iv-loop diuretics during the 6-month clinical follow-up duration
- Safety: The number of occurrences of acute kidney injury (defined as a 50% decline in estimated glomerular filtration rate relative to baseline, or decrease of >30 ml/min/1.73m2 and to a value below 60 ml/min/1.73m2 during the 6-month clinical follow-up duration)
- Safety: The time to the first occurrence of acute kidney injury (defined as a 50% decline in estimated glomerular filtration rate relative to baseline, or decrease of >30 ml/min/1.73m2 and to a value below 60 ml/min/1.73m2 during the 6-month clinical follow-up duration)
- Serum biomarkers (NT-proBNP, sodium, osmolality, haemoglobin, haematocrit) at 3 months after randomisation
- Weight at 3 months after randomisation
- Use of concomitant medication (diuretics in particular)

 $^{^{1}}$ The KCCQ, TDS-HF and EQ-5D-5L are scored according to 'Appendix 2: Scoring of the Questionnaires'.

2.4. Intervention

Patients will be randomised to standardized lifestyle advice by the treating physician and/or nurse practitioner of either liberal fluid intake (no restrictions, fluid intake as desired) or fluid restriction of 1500 ml/day for a period of 3 months. Other lifestyle interventions (e.g., sodium restriction or activity) remain unadjusted. The latter is emphasized during the standardized lifestyle advice.

Fluid restriction of 1500 ml/day is considered standard clinical practice, and liberal fluid intake is considered the investigational treatment.

2.5. Randomisation and blinding

Randomisation takes place after the patient is eligible according to the inclusion and exclusion criteria and has provided informed consent and completed the QoL questionnaires. Patients are randomised 1:1 to either liberal fluid intake or standard fluid restriction using Castor EDC with a random block randomisation algorithm and stratified randomisation per each including centre. A patient cannot be randomised more than once in the study.

Members of the steering committee and Event Adjudication Committee (EAC) members are blinded to randomisation.

The coordinating investigator (JH) and DSMB members are not blinded. The coordinating investigator (JH) prepares the data overview for the statistician of the DSMB who performs the interim analysis. The data overview is not shared with the members of the steering committee or EAC members.

2.6. Sample size

Sample size calculation was performed with the software package G*Power 3.1.7 and performed as previously described methods for repeated measures ANCOVA analysis, using baseline QoL as a covariate (1).

For our sample size calculation, a correlation of 0.88 between baseline and follow-up KCCQ-OSS was assumed (2). Furthermore, a follow-up KCCQ-OSS of 66.25 with a standard deviation of 20 was assumed for liberal fluid intake group (3-7). Next, we assume a 2.5-point difference in KCCQ-OSS follow-up scores at 3 months between both randomisation groups (3-7). To test this difference at a p-value of 0.05 and power of 80%, we need a total of 454 evaluable patients. Anticipating a drop-out rate of 10% we aim to enrol 506 patients.

To interpret the clinical relevance of a mean difference of 2.5 points in KCCQ score, it is important to differentiate between differences in scores on a patient level or group level. Based on previous validation studies on a patient level, a change of 5, 10 and 20 points in KCCQ-OSS follow-up scores are considered small, moderate-to-large and large-to-very large clinical important changes respectively (8, 9). Moreover, even smaller changes are possibly associated with clinically important improvements or deteriorations (10). However, a mean difference on randomisation group level is not directly comparable with the clinically important changes on a patient level. Randomisation group means reflect many different outcomes amongst patients, as in each randomisation group patient's clinical status will improve, deteriorate or remain stable.

In view of the above, it is illustrative to look at the results of previous landmark trials which demonstrated positive effects on clinical outcome for the studied interventions, which are now part of guideline-directed medical therapy.

For example, in the PARADIGM-HF (sacubitril/valsartan versus enalapril), the KCCQ-OSS mean difference was 1.27 points, while the proportion of clinically important improvements was greater and the proportion of deterioration was lower for sacubitril/valsartan group compared to the enalapril group (35% versus 33% and 27% versus 31%, respectively) (7).

The same applies for the DELIVER trial (dapagliflozin versus placebo) where the mean KCCQ-OSS was 2.1 points higher at follow-up in the dapagliflozin group (P<0.001) while on a patient level less patients experienced deterioration (>5 points worse) (21% versus 25%) and more patients had 10+ and 15+ points improvement (40% versus 36% and 28% versus 25%, respectively) (11). Also in the SHIFT-HF (ivabradine versus placebo), the proportions of clinically important changes on patient level were in favour of ivabradine, although not significant, the KCCQ-OSS mean difference was 2.4 points higher in the ivabradine group (P<0.001) (4).

In light of these trials, we consider a statistically significant 2.5-point mean difference in KCCQ-OSS follow-up scores between study groups as clinically relevant, which is very likely to represent clinically relevant differences on a patient level.

This sample size also allows adequate power to asses a 1.5-point difference in thirst distress at 3 months between both randomisation groups (mean score of 16 with a standard deviation of 8 and intraclass correlation of 0.88; p-value: 0.05 and power: 80%).

3. Statistical analysis

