3.10. Analysis of the primary outcome

3.10.1. Main analysis

The difference between the two treatment arms in QoL after 3 months, as assessed with KCCQ-OSS, will be tested with the use of an ANCOVA analysis, using baseline QoL as a covariate. The difference will be presented as the average treatment effect for liberal fluid – restricted fluid arm. The estimated difference will be presented with a point estimate and 95% confidence interval. A p-value of <0.05 will be considered significant.

For the primary analysis, the intention-to-treat principle will be applied.

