3.10.2. Adjusted analyses

Not applicable.

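### The 80% power holds only at a baseline to 3-month correlation of 0.88 and falls quickly below it; the primary ANCOVA could recover some precision by including centre, the randomisation stratum

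*SAP*

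**What the plan says.** SAP 2.6 bases the sample size on an ANCOVA of 3-month KCCQ-OSS with the baseline score as covariate. Its inputs are:

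- "a correlation of 0.88 between baseline and follow-up KCCQ-OSS was assumed"
- "a follow-up KCCQ-OSS of 66.25 with a standard deviation of 20 was assumed for liberal fluid intake group"
- "we assume a 2.5-point difference in KCCQ-OSS follow-up scores at 3 months between both randomisation groups"

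The result is: "To test this difference at a p-value of 0.05 and power of 80%, we need a total of 454 evaluable patients". With 10% drop-out the target becomes 506. No other correlation is considered.

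To argue that 2.5 points is clinically relevant, the same section quotes responder shares from two trials:

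- **DELIVER:** 21% against 25% worsened by more than 5 points, and "more patients had 10+ and 15+ points improvement (40% versus 36% and 28% versus 25%, respectively" for dapagliflozin and placebo.
- **PARADIGM-HF:** 35% against 33% improved and 27% against 31% deteriorated. No cut-off is given.

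SAP 2.5 stratifies the 1:1 randomisation by centre. SAP 3.10.1 adjusts the primary ANCOVA for baseline KCCQ-OSS only, and the entry under 3.10.2 (adjusted analyses) is "Not applicable".

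**The concern.** In an ANCOVA the residual variance is proportional to 1 − r². Near r = 0.88 a small drop in r raises it sharply: 1 − r² is 0.226 at 0.88 and 0.360 at 0.80. A single power figure hides this. The DELIVER shares also describe individual changes that are more widely spread than r = 0.88 with SD 20 would produce under a normal model.

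If r is lower than assumed, a non-significant primary result is more likely than the plan says and could be read as no effect. Under SAP 3.3 the primary and key secondary endpoints are tested hierarchically, so a miss on KCCQ-OSS would also stop confirmatory testing of thirst distress. In that setting it is wasteful to leave the stratification factor out of the primary model.

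**Working it through.** **Inputs.** From SAP 2.6: r = 0.88, SD = 20, difference 2.5, alpha 0.05, power 80%, 454 evaluable. From SAP 2.5: 1:1 allocation, so 227 per arm. Section 2.6 does not state sidedness; two-sided is taken from 3.10.1 ("The estimated difference will be presented with a point estimate and 95% confidence interval. A p-value of <0.05 will be considered significant").

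**1. The plan's own figure.** Residual SD = 20√(1 − 0.88²) = 9.50. Per arm, n = 2(1.96 + 0.8416)² × 9.50² / 2.5² = 226.7, so 227 and 454 in total. SE = 9.50√(2/227) = 0.892, and power = Φ(2.5/0.892 − 1.96) = 80.1%. Then 454/0.9 = 504.4, so 505, or 506 for equal arms. Both figures reproduce.

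**2. Dependence on r**, with 227 per arm and SD 20:

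| r | Residual SD | SE | Power | 95% CI half-width (1.96 × SE) |
|---|---|---|---|---|
| 0.88 | 9.50 | 0.892 | 80% | 1.75 |
| 0.85 | 10.54 | 0.989 | 72% | 1.94 |
| 0.80 | 12.00 | 1.126 | 60% | 2.21 |
| 0.75 | 13.23 | 1.242 | 52% | 2.43 |

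**3. What the quoted shares suggest.** With equal variances, SD of change = 20√(2(1 − r)), which is 9.80 at r = 0.88; inversely, r = 1 − SD²/800. Under normality, SD of change = (gap between two cut-offs) / (gap between the matching normal quantiles).

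| Arm and cut-offs | SD of change | r | Power |
|---|---|---|---|
| DELIVER dapagliflozin, −5 and +10 | 15/(0.253 + 0.806) = 14.2 | 0.75 | 52% |
| DELIVER dapagliflozin, −5 and +15 | 20/(0.583 + 0.806) = 14.4 | 0.74 | 51% |
| DELIVER placebo, −5 and +10 | 15/(0.358 + 0.674) = 14.5 | 0.74 | 50% |
| DELIVER placebo, −5 and +15 | 20/(0.674 + 0.674) = 14.8 | 0.73 | 49% |
| PARADIGM-HF sacubitril/valsartan, ±5 assumed | 10/(0.385 + 0.613) = 10.0 | 0.875 | 78% |
| PARADIGM-HF enalapril, ±5 assumed | 10/(0.440 + 0.496) = 10.7 | 0.857 | 73% |
| PARADIGM-HF sacubitril/valsartan, ±4.5 assumed | 9/(0.385 + 0.613) = 9.0 | 0.898 | 86% |
| PARADIGM-HF enalapril, ±4.5 assumed | 9/(0.440 + 0.496) = 9.6 | 0.884 | 81% |

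Rounding alone also matters. Sacubitril/valsartan shares of 34.5% and 26.5%, which round to the quoted 35% and 27%, give r = 0.881 at ±5.

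In the other direction, take a change SD of 9.80 and 28% improving by 15 or more. The mean change is then 15 − 0.583 × 9.80 = 9.29, and the share worsening by more than 5 is Φ((−5 − 9.29)/9.80) = 7%. DELIVER is quoted at 21%.

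**4. How firm the DELIVER inference is.**

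- *SD in DELIVER.* It is not given. At 18, 22 or 24 the implied r is 0.66–0.69, 0.77–0.79 or 0.81–0.83. Keeping r = 0.88 would need an SD of 14.2/√0.24 = 29 to 14.8/√0.24 = 30.
- *Shape.* A flat distribution has SD = (gap / share between the cut-offs)/√12. That runs from (15/0.39)/√12 = 11.1 to (20/0.50)/√12 = 11.5, so r is 0.83 to 0.85. With no distributional assumption, the shares force an SD of change of only about 7.0 to 7.2, which is below 9.80.

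**5. If all 506 contribute** (253 per arm, an upper bound because imputed outcomes carry less information than observed ones): at r = 0.88, SE = 9.50√(2/253) = 0.845 and power is 84%. At r = 0.75, SE = 13.23√(2/253) = 1.176 and power is 57%.

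**6. What extra covariates would have to do.** To bring the residual variance at r = 0.75 down to its value at 0.88, they would need to explain 1 − 0.2256/0.4375 = 48% of what baseline KCCQ-OSS leaves unexplained.

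**The case against.** The strongest reply is that nothing in the documents shows 0.88 to be wrong, and that reply stands.

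- A reader might infer that 2.6 contradicts itself. It does not. The DELIVER shares give no correlation or SD, and without a distributional assumption they are compatible with 0.88 (step 4). They are quoted to illustrate clinical relevance, not to support the variance inputs.
- A reader might infer that every quoted arm lies below 0.88. That depends on a PARADIGM-HF cut-off that the SAP does not state. At 4.5 points both arms are above 0.88, and within rounding one arm is above it even at 5.
- A reader might take about 50% as the real power. That figure rests on one trial, whose listed title restricts it to preserved or mildly reduced ejection fraction, while this trial also plans an HFrEF subgroup (3.10.3). DELIVER's follow-up time is not given, and a longer interval would lower its correlation. Here the interval is 3 months, and recent HF admission and recent therapy changes are exclusions (2.2.2), which plausibly raises r.
- A reader might extend the doubt to the thirst calculation, which uses an "intraclass correlation of 0.88". That has no consequence. With 1.5 points and SD 8, power at r = 0.73 is Φ(1.5/(8√(1 − 0.73²)√(2/227)) − 1.96) = 83%, and it is 99% at 0.88.
- Adjusting for baseline alone is a legitimate prespecified choice, and the planned 95% CI will show the precision actually achieved.

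The reply does not remove the steep dependence of power on r, the absence of any range in 2.6, or the mismatch between the randomisation and the primary model.

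**Conclusion.** The sample size is arithmetically correct for its inputs, but the 80% is conditional on r = 0.88. At SD 20 and 2.5 points, power is about 72% at 0.85, 60% at 0.80 and 52% at 0.75, and the expected CI half-width widens from 1.75 to 2.43 points, close to the target difference itself.

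Of the two trials whose shares can be used, one suggests 0.73 to 0.75 (normal changes and SD 20 assumed) and the other is roughly consistent with 0.88 (0.86 to 0.90 for cut-offs of 4.5 to 5 points). The value looks optimistic; it is not refuted, and no single lower power figure should be quoted in place of 80%.

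The firm part is the model: randomisation is stratified by centre and the primary ANCOVA omits it. If centres differ in outcome after adjustment for baseline, that variance stays in the error term and the standard error does not reflect the stratified design.

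**What to change.** 1. **SAP 3.10.1:** fit the primary ANCOVA with baseline KCCQ-OSS and centre. Optionally add a small fixed set of baseline variables already collected (for example NYHA class and log NT-proBNP, both listed in 3.7), named before unblinding. Amend 3.10.2 to agree, and include the same variables in the imputation model in 3.10.4.
2. **SAP 2.6:** say that 454 evaluable patients give 80% power if r = 0.88, and about 72%, 60% and 52% at 0.85, 0.80 and 0.75. Add that power at 0.88 is at most 84% if all 506 patients contribute.

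**Cost:** a short SAP amendment and a few degrees of freedom (three for the four centres mentioned in the Protocol's response letter, more if centres were added). No extra patients or data are needed. The stated power becomes less favourable. The precision gain cannot be computed from the documents, and it should not be presented as a remedy for a correlation near 0.75: step 6 shows how much the added terms would have to explain.
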